### **MRI/CT of the Brain**

MRI of the brain will be assessed at protocol-specified time points as outlined in the [Appendix C](#) and [Appendix D](#), Study Activities Tables. Brain MRI may be substituted by CT with intravenous contrast at the discretion of the investigator if MRI testing is clinically contra-indicated or not available. MRI/CT of the brain is required after screening only when clinically indicated (e.g., CNS metastasis history and if CNS progression is suspected).

### **Randomization and Subject Number Assignment**

An Interactive Response Technology system (IRT) will be utilized to register subjects.

Subjects who complete all Screening procedures and meet the eligibility criteria will proceed to randomization. Refer to Section 5.5.5 for details associated with subject assignment to treatment arms.

### **Patient Reported Outcomes (PRO)**

Health-related quality of life and symptom assessments will be performed per [Appendix C](#) and [Appendix D](#), Study Assessments using the EORTC QLQ-C15-PAL, the EORTC QLQ-LC13, and the European Quality of Life-5 Dimensions (EQ-5D-5L).

The European Organization for Research and Treatment of Cancer Quality of Life Questionnaire (EORTC QLQ-C15-PAL) is a shortened version of the EORTC QLQ-C30, a widely used instrument for measuring QOL in cancer research. It was developed to ease the difficulty of completing long surveys in subjects who may have a high

symptom burden and short life expectancy. The QLQ-C15-PAL questionnaire contains four multi-item scales (physical & emotional functioning, fatigue and pain) along with six individual items (nausea & vomiting, dyspnea, insomnia, appetite loss, constipation, and global quality of life).

The EORTC QLQ-LC13 is a lung cancer specific module which will supplement the EORTC QLQ-C15-PAL, resulting in a 28-item disease and cancer site-specific quality of life and symptom questionnaire. The QLQ-LC13 module items evaluate symptoms such as cough, haemoptysis, shortness of breath, sore mouth or tongue, dysphagia, tingling hands or feet, hair loss, and pain.

The EuroQol 5 Dimensions 5 Level (EQ-5D-5L) is a generic preference instrument that has been validated in numerous populations. The EQ-5D-5L is composed of 5 questions and a visual analog scale (VAS) assessing overall health that can be converted into a single health status or "utility" score for use in an economic evaluation to adjust life-years gained by the subject's health-related quality of life.

#### **Fluid Retention Questionnaire (Including Subject Daily Weight)**

Throughout the treatment period as outlined in the [Appendix C](#) and [Appendix D](#), Study Activities Tables, subjects will be asked about the development of any new or worsening peripheral edema or dyspnea ([Appendix J](#), Fluid Retention Questionnaire). The Arm A assessments on Cycle Days 8, 15, 29 and 36 may take place by phone, with the site contacting the subject and reviewing the questionnaire.

Starting on Day 1 through the EOT visit, subjects in Arm A will maintain a diary of daily weight (captured on the Fluid Retention Questionnaire). Subjects should be instructed to use a consistent device throughout the study. The site should advise the subjects in cases where sudden weight gain is observed; the subject should contact the site and possibly be assessed in the clinic.

**Additional Two Cycles of Rovalpituzumab Tesirine (Arm A only)**

Up to two additional cycles of rovalpituzumab tesirine may be permitted, however the last dose on study must be administered no later than 04 December 2019 for subjects in Arm A who provide consent and who satisfy all of the following criteria:

- achieved clinical benefit defined as stable disease or better with two initial cycles of rovalpituzumab tesirine
- have findings indicative of disease progressing (not limited to CNS) at least 12 weeks after the second dose of rovalpituzumab tesirine
- received no other systemic anti-cancer therapy after two initial cycles of rovalpituzumab tesirine
- had no prior on-study serosal effusions (Appendix I) or edema of > Grade 2 or other non-hematological treatment-related AEs of  $\geq$  Grade 3 or potential DILI and any treatment-related AEs have resolved to Grade 1 or baseline
- have no clinically significant symptoms or signs related to disease progression and/or indicating threat to vital organs and no disease progression at critical anatomical sites necessitating urgent alternative treatment
- have no decline in performance status as compared to the last radiographic assessment at which no progressive disease was identified

Any new or progressing CNS disease of such subject must be definitively treated (radiotherapy or surgery) in order for the subject to be eligible for the two additional cycles of treatment. Subjects remaining in rovalpituzumab tesirine treatment post-progression not limited to CNS will be followed radiographically until the second event of progressive disease. CT/MRI scan must be performed within one week prior to the 4th dose of rovalpituzumab tesirine.

Subjects who do not provide consent for two additional doses of rovalpituzumab tesirine should proceed to the End of Treatment (EOT) visit before continuing on to the Survival Follow Up period.

The last radiographic assessment prior to additional doses of rovalpituzumab tesirine will be used as a new baseline for purposes of subsequent disease assessment.

### **End of Treatment (EOT) Visit**

The visit during which an investigator identifies radiographic disease progression or the subject is not eligible for two additional doses of rovalpituzumab tesirine (Arm A only), or a subject meets other criteria for study treatment discontinuation will be considered the EOT Visit. The EOT visit is the last visit during the treatment phase before a subject enters the Post Treatment Follow Up and/or Survival Follow Up period. The EOT visit should occur within 7 days of documentation of the decision to discontinue treatment and prior to subjects beginning any new anti-cancer therapy, if possible. The reason(s) for the discontinuation from study treatment will be recorded and assessments will be performed per [Appendix C](#) and [Appendix D](#), Study Activities Tables.

Disease/Response assessment, including MRI/CT if clinically indicated, may be omitted if performed within the last 6 weeks.

### **Post-Treatment Follow Up (PTFU)**

For all subjects without disease progression (including those who discontinue study treatment for reasons other than disease progression), the first follow-up visit will occur at 6 weeks ( $\pm$  1 week) after the last Disease/Response Assessment, then every 6 weeks ( $\pm$  1 week) until disease progression or initiation of new anti-cancer therapy, whichever occurs first. Refer to [Appendix C](#) and [Appendix D](#), Study Activities Tables for details of required assessments.

At progression, an optional fresh tumor material sample may be collected from subjects who have provided consent (Section 5.3.1.2, Collection and Handling of Biomarker and Optional Exploratory Research has details regarding tumor material at Time of Disease Progression).

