Subjects will be stratified by prior history of brain metastases (yes vs. no), prior PCI (yes vs. no) for subjects with no prior history of brain metastases, sensitivity to first line platinum-based regimen [sensitive (OR/SD after first line therapy and progression/recurrence-free interval  $\geq$  90 days) vs. refractory/resistant (PD as best response or  $<$  90 days progression/recurrence-free interval after first line therapy)] and LDH level ( $>$  ULN vs.  $\leq$  ULN) at screening.

[figure not shown]
Post-baseline radiographic assessments will be performed every 6 weeks for the first 30 weeks and then every 9 weeks until radiographic progression or death. Radiographic information will be collected to determine response according to Response Evaluation Criteria in Solid Tumors (RECIST) version 1.1. For subjects receiving post-progression doses of rovalpituzumab tesirine radiographic assessments will continue until the second event of disease progression as outlined in Section 5.3.1.1.

If a subject is discontinued from the study with an ongoing adverse event or an unresolved clinically significant laboratory result, the site will attempt to provide follow-up until a satisfactory clinical resolution of the laboratory results or adverse event is achieved.

Subjects no longer undergoing clinical assessments will have survival information reported approximately every 6 weeks (or as requested by sponsor to support data analysis) beginning at the last clinical assessment and continuing until the endpoint of death, the subject has become lost to follow-up, or termination of the study by AbbVie.

A schematic of the study is provided in [Figure 1](#), Study Schema.

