Scheduled radiographic assessments will not be affected by delays in therapy and/or drug holidays. Subjects will continue to be monitored by the same diagnostic method throughout the study every 6 weeks after randomization for the first 30 weeks and then every 9 weeks until radiographic disease progression. Subjects who discontinue treatment for reasons other than radiographic disease progression will continue to be followed according to the above schedule, until disease progression occurs.

For subjects in Arm A, if the investigator chooses to continue treating the subject post-progression and the subject consents to additional doses of rovalpituzumab tesirine, scans will continue to be collected every 6 weeks for the first 30 weeks from additional Cycle 3 Day 1 and then again every 9 weeks until the second event of progressive disease. If clinically indicated, radiographic assessments may be performed at times other than those indicated in [Appendix C](#) and [Appendix D](#).

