Objective response rate includes confirmed complete response (CR) and confirmed partial response (PR) assessed by the CRAC based on RECIST v1.1 from the date of randomization until disease progression or death, whichever comes first. A subject who did not meet CR or PR, including those who did not have post-baseline radiological assessments will be considered as non-responder.

Comparison of ORR will be carried out using a one-sided Cochran-Mantel-Haenszel (CMH) test, stratified by the randomization stratification factors. Odds ratio will be presented with two-sided 95% CI. The difference in ORR will be provided with two-sided 95% CI. Rates and corresponding 95% exact CI will be calculated by Clopper-Pearson method for each arm. Sensitivity analysis based on investigator-determined ORR will also be performed.

Clinical benefit includes complete response (CR), partial response (PR), and stable disease (SD) assessed by the CRAC based on RECIST v1.1 from the date of randomization until disease progression or death, whichever comes first. A subject who did not meet CR, PR, or SD, including those who did not have post-baseline radiological assessments, will be considered as non-responder. The same statistical methodology will be used as that for ORR endpoint.

A sensitivity analysis of ORR and CBR will be performed, accounting for subjects who initiated a new anti-cancer therapy. Modified endpoints of ORR and CBR, defined as rates of response from the date of randomization until initiation of new anti-cancer therapy/procedure, disease progression, or death, whichever comes first, will be analyzed using the same methodology as that for the endpoints of ORR and CBR.

Only subjects with an objective response will be included in the analysis of duration of response (DOR). DOR is defined as the time between the date of first response (CR or PR by CRAC, whichever is recorded first) to the date of the first documented tumor progression (assessed by CRAC per RECIST 1.1) or death due to any cause, whichever comes first. If a subject is still responding (i.e., has not progressed nor died after CR or PR), then the subject's data will be censored at date of the last radiographic assessment by CRAC. Methods for DOR analysis are similar to those described for the OS endpoint.

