11.2 Efficacy Analyses

Overall Survival (OS)

All events of death available at the time of analysis will be included, regardless of whether the event occurred while the subject was still taking study drug or after the subject discontinued study drug.

The primary endpoint OS will be compared between treatment Arms rovalpituzumab tesirine and topotecan at both interim and final analysis. Superiority of rovalpituzumab tesirine (Arm A) to topotecan (Arm B) in terms of OS will be evaluated using stratified log-rank test, adjusting for the study stratification factors.

This stratified log rank test will be implemented in SAS using LIFETEST procedure as follows:

```
proc lifetest method=km;  
  time <follow-up time>*<Censoring status>(<censoring codes>);  
  strata <stratification factors> / group=<treatment>  
      test = logrank;  
run;
```

The OS curves for each arm will be estimated using the Kaplan-Meier (KM) product-limit method. Two-sided, 95% confidence interval for median OS will be computed, using the Brookmeyer and Crowley method. Landmark survival rate, defined as the survival rate estimated using the Kaplan-Meier approach at pre-defined time points from randomization (e.g., 6, 12, 18, and 24 months), will be presented with two-sided 95% CIs, using Greenwood's method for calculating standard errors.

Estimation of HR

A Cox proportional-hazards regression model⁴ with the treatment and stratification factors as covariates will be used to estimate the HR of rovalpituzumab tesirine to topotecan and its two-sided 95% CI. Only the main effects of the stratification variables will be fitted.

Where, treatment takes value 1, if treated with rovalpituzumab tesirine, otherwise 0, for topotecan. Efron's approximate method (1977) will be used for handling ties. In SAS, estimate of HR will be estimated using PHREG procedure and Efron's method⁵ will be employed by using TIES = EFFRON option in MODEL statement.¹⁹ Following SAS code will be used

```
PROC PHREG;  
  CLASS <treatment>;  
  MODEL <follow-up time>*<Censoring status>(<censoring codes>)=  
<strata variables> <treatment> /TIES=EFFRON RL;  
RUN;
```

Progression-free Survival (PFS)

All disease progression assessed by CRAC per RECIST v1.1 will be included, regardless of whether the event occurred while subject was taking the study drug or had previously

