discontinued the study drug. Data from subjects who are lost to follow-up will be included in the analysis as censored observations on the last date of radiographic assessment that the subject was documented to be progression free.

Analysis methods for PFS endpoint are similar to those described for the OS endpoint. The PFS rates at 6, 9 and 12 months and corresponding 95% CIs will also be estimated using KM estimates on the PFS curve for each arm.

Clinical Benefit Rate (CBR)

Subjects with clinical benefit includes those who achieve confirmed complete or partial response (CR or PR), or stable disease (SD) for at least 12 weeks (2 tumor assessments) as adjudged by the CRAC based on RECIST v1.1.

The clinical benefit rate (CR, PR, and SD) rate will be reported with exact (binomial) two-sided 95% CI for each treatment arm.

CBR will be compared between treatment arms using a Cochran-Mantel-Haenszel (CMH) test, stratified by the randomization stratification factors. The difference in CBR will be summarized with two-sided 95% CI. Rates and corresponding 95% exact CIs will be calculated by Clopper-Pearson method for each arm. Sensitivity analysis based on investigator-determined CBR will also be performed.

Objective Response Rate (ORR)

Analysis of ORR will be performed for the randomized subjects with measureable disease at baseline.

Objective response includes complete response (CR) and partial response (PR) assessed by the CRAC based on RECIST v1.1. Subjects who do not achieve CR or PR, including those who do not have post-baseline radiological assessments will be considered as non-responders.

The same statistical methodology will be used as that for CBR endpoint.

Duration of Response (DOR)

Only subjects with a confirmed objective response will be included in the analysis of duration of response (DOR).

DOR is defined as the time between the date of first response (CR or PR by CRAC, whichever is recorded first) to the date of the first documented tumor progression (assessed by CRAC) or death due to any cause, whichever comes first. If a subject is still responding (i.e., has not progressed nor died after CR or PR), then the subject's data will be censored at date of the last radiographic assessment by CRAC. For subjects who never experienced CR or PR, these subjects' data will not be included in the duration of response analysis.

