11.3 Sensitivity Analyses

Sensitivity analyses will be conducted to evaluate the robustness of efficacy results. OS and PFS (by CRAC) will be analyzed in the PPS.

A sensitivity analysis of PFS will be performed based on investigator-assessed disease progression or death from any cause using the Randomized Set. The statistical methodology described in Section 11.1.1 for TTE endpoints will be used.

Sensitivity analyses of investigator-determined ORR will also be performed based on the Randomized Set (ORR analysis will only include the randomized subjects with measurable disease at baseline).

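### Scan-stop rules conflict over new anti-cancer therapy, and the SAP omits the protocol's new-therapy sensitivity analyses and its response window

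*Protocol*

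**What the plan says.** **When scans stop.** Protocol 5.3.1.1, Post-Treatment Follow Up, has progression-free subjects seen every 6 weeks "until disease progression or initiation of new anti-cancer therapy, whichever occurs first". Appendix C note c and Appendix D note b give the same stop. The imaging text of 5.3.1.1 says instead that subjects who leave treatment for reasons other than radiographic progression "will continue to be followed according to the above schedule, until disease progression occurs". Protocol 5.1 scans every 6 weeks for 30 weeks, "then every 9 weeks until radiographic progression or death". Protocol 5.4.1 also runs to progression, and Appendix C note s and Appendix D note r run to progression or death. None of these names new therapy as a stop.

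**PFS.** Protocol 8.1.5 defines the event as progression or death from any cause, with no censoring at new therapy in the main analysis. SAP 11.2 says: "All disease progression assessed by CRAC per RECIST v1.1 will be included, regardless of whether the event occurred while subject" was on study drug or had left it. It has no new-therapy rule.

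**Sensitivity analyses.** Protocol 8.1.5 adds a PFS analysis censored at the last central scan on or before new therapy. For response it says: "A sensitivity analysis of ORR and CBR will be performed, accounting for subjects who initiated a new anti-cancer therapy". SAP 11.3 lists OS and PFS in the Per-protocol Set (PPS), investigator-assessed ORR, and this: "A sensitivity analysis of PFS will be performed based on investigator-assessed disease progression or death from any cause using the Randomized Set". SAP 11.2 adds investigator-assessed CBR. None addresses new therapy.

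**Response window.** Protocol 8.1.5 counts ORR and CBR from randomization until progression or death. SAP 11.2 says only: "Objective response includes complete response (CR) and partial response (PR) assessed by the CRAC based on RECIST v1.1". Its CBR definition has no end either. For Arm A subjects given additional cycles after progression, the last prior scan "will be used as a new baseline for purposes of subsequent disease assessment", and scanning continues to a second progression.

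**The concern.** A progression-free subject who starts new therapy falls under two rules that a site cannot both follow. Survival follow-up does not settle it: Protocol 5.3.1.1 names progression, or stopping treatment and declining scans, as the ways in, not new therapy.

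If scanning stops, progression can no longer be seen but death still counts, so that subject's PFS time runs on to death. Equal switching lengthens PFS in both arms; unequal switching distorts the comparison. Unequal rates are plausible because Arm A has a fixed two-cycle course and Arm B is treated to progression, so more Arm A subjects can be off treatment without progression.

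The protocol foresaw this and planned checks. The SAP omits them without giving a reason. Separately, an open-ended response window leaves room to count a response that follows progression, which the retreatment option makes possible in Arm A only.

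**Working it through.** **1. The plan's own figure.** The documents state no sample size or power for PFS or ORR. The OS event count reproduces: (1.960 + 1.036)² / [(2/3)(1/3)(ln 0.75)²] = 488.2, rounded up to 489 deaths as in Protocol 8.4. Nothing below changes it.

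**2. Inputs for a PFS illustration.** From the documents: 2:1 allocation; median PFS 2.7 months and OS 6.5 months on topotecan (Protocol 3.1); 6-weekly scans. Assumed: exponential progression with median 2.7 months in both arms (true ratio 1.00); exponential time from progression to death with median 3.8 months; new therapy before progression in 5–20% per arm, starting between 20% and 100% of the way to progression; cut-off uniform between 14 and 36 months; 300,000 simulated subjects.

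**3. PFS hazard ratio, Arm A over Arm B.**

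| New therapy before progression, A / B | Scans continue to progression | Scans stop, later deaths count | Censored at last scan before new therapy |
|---|---|---|---|
| 10% / 10% | 1.00 | 1.00 | 1.00 |
| 20% / 10% | 1.00 | 0.91 | 0.95 |
| 20% / 5% | 1.00 | 0.87 | 0.94 |
| 10% / 20% | 1.00 | 1.09 | 1.04 |
| 5% / 20% | 1.00 | 1.15 | 1.07 |

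At equal 10% rates the ratio is unbiased, but mean PFS time rises from 4.5 to 4.9 months in both arms. Censoring at new therapy reduces the bias without removing it, because in this model switching tends to come shortly before progression. Counts by arm are therefore needed beside the sensitivity analysis.

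**4. The 3.8-month assumption.** It is 6.5 − 2.7, but medians do not subtract, and the model then has a median OS of about 7.8 months. A median of 2.7 months to death reproduces 6.5. Re-running the four unequal scenarios with it narrows the third column to about 0.90 to 1.11.

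**5. ORR, retreatment.** Added Arm A points = share retreated × response to retreatment. With an assumed 5–20% retreated and the 16% response rate that Protocol 3.3 gives for third-line subjects: 0.05 × 16 = 0.8 to 0.20 × 16 = 3.2 points. These are upper figures, since a retreated subject who had already responded adds nothing.

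**6. CBR, retreatment.** Protocol 5.3.1.1 requires stable disease or better on the first two cycles and progression at least 12 weeks after the second dose. Most retreated subjects would already count, so little is added.

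**7. ORR, new therapy.** If scans continue after new therapy, added points = share switching × response to it: 0.05 × 10 = 0.5 to 0.20 × 20 = 4.0 points (both factors assumed). The protocol's main window, which ends at progression or death, allows these responses too. Only its sensitivity analysis removes them.

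**The case against.** **Most scan text already favours progression.** The follow-up section sets a visit schedule, whereas the passages specifically about scanning run to progression. On that reading the ratio stays at about 1.00. This stands as a limit on likelihood: the bias arises only where sites follow the follow-up section and the two activity-table notes. Those are current text, so it remains possible.

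**The PFS and ORR problems need opposite readings.** Lost progressions require scans to stop at new therapy; responses to new therapy require them to continue. This is right, and the two should not be added. The retreatment issue depends on neither, because retreated subjects are scanned to a second progression.

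**The SAP has a partial check.** The PPS excludes subjects with an excluded concomitant treatment (SAP 6.0), and Protocol 5.2.3.4 prohibits other systemic anti-neoplastic therapy during the study. A reader might infer from SAP 11.3 that nothing bears on the question; that is too strong. But the PPS drops whole subjects instead of censoring them, is not applied to ORR or CBR, and may miss therapy started more than 70 days after the last dose, which SAP 8.3 does not class as concomitant.

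**The SAP implies that response precedes progression.** Its duration of response runs from first response to first documented progression, which makes no sense for a response after progression. That supports the intended meaning but does not define the ORR numerator. ORR is also only exploratory in the SAP.

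**Amendment 4 limits the consequence.** Protocol 8.0 cancels efficacy testing and allows endpoints with too little data to be summarised only; central review is withdrawn. This stands. Protocol 8.0 still has efficacy endpoints analysed by the original methods as appropriate, so PFS and response estimates may be reported.

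**Conclusion.** The concern holds as a conflict within the protocol and a gap between protocol and SAP. The scan-stop passages disagree, PFS has no new-therapy rule, the SAP omits the planned new-therapy analyses, and its response definitions lose their end point.

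Under the stated assumptions, a true PFS hazard ratio of 1.00 could be reported as 0.87 to 1.15 if scans stop at new therapy and switching differs by arm. It stays at 1.00 if rates are equal or scanning continues. A shorter time from progression to death narrows the range. Retreatment could add at most 0.8 to 3.2 points to Arm A's ORR under the assumed shares.

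Three stronger readings are tempting. One is that the bias favours rovalpituzumab tesirine because Arm A stops treatment by design. The documents make unequal switching plausible but give no rates, so the direction is not known. Another is that restoring the protocol's response window would exclude responses after new therapy; it would exclude only those after progression. The third is that a trial conclusion is at risk. No efficacy test remains, OS is unaffected, and the consequence is confined to reported PFS, ORR and CBR estimates.

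**What to change.** - **Protocol:** reconcile the Post-Treatment Follow Up text, Appendix C note c and Appendix D note b with 5.1, the imaging text of 5.3.1.1, 5.4.1 and the scan notes, so that scan collection matches the PFS definition.
- **SAP 11.3:** add PFS censored at the last scan on or before new therapy, and ORR and CBR counted only until new therapy, progression or death. Use investigator assessments where central review is no longer available. If these analyses are deliberately dropped, say why.
- **SAP 11.2:** restore the window from randomization until progression or death for ORR and CBR, and state how PFS handles new therapy.
- **Reporting:** tabulate new therapy before documented progression by arm.

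The cost is a wording change, SAP text and a few tables. Protocol 5.3.1.1 already collects dates of subsequent therapy in survival follow-up. The sensitivity analysis will have fewer PFS events, and scans that sites have already skipped cannot be recovered.
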